This study proposes to explore the efficacy of metformin to reduce liver fat using novel and minimally invasive imaging and biomarkers in a pilot randomized double-blind placebo-controlled trial.

Study Design:

Eligibility Criteria: PCOS subjects who participated in a previous baseline study and have liver fat greater than or equal to 4.8% by MRS or evidence of insulin resistance (on an oral glucose tolerance test) will be invited to participate in this study with the goal of recruiting 44 subjects who are 13 to 25 years at least two years post-menarche. Oligomenorrheic subjects will complete the protocol during the early follicular phase of the menstrual cycle (days one through seven) and amenorrheic subjects will complete the protocol on any day. **Exclusion criteria:** 1. Presence or history of a medical disorder (e.g. non-classical CAH) or medication known to affect body composition, insulin secretion and sensitivity, or the GH-IGF1 axis (i.e. use of glucocorticoids or thyroid hormone), excessive alcohol use, liver disease (other than NAFLD) indwelling hardware, current or past pregnancy and use of metformin or hormonal contraception within 3 months of enrolling in the previous study.

The protocol will comprise:

- a) Randomization: Subjects whose liver fat is 4.8% or greater or have evidence of insulin resistance on an oral glucose tolerance test (n=22) will be randomized to placebo or extended-release metformin (XR) (500 mg (1 tablet) once a day for one week and then 1000 mg (2 tablets) daily for six months). Randomization will be double-blind and will be performed by randomly selected permuted size 2 and size 4 blocks determined by the CUMC Research Pharmacy with the guidance of a statistician and will be stratified based on presence or absence of insulin resistance.

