1. Change in liver fat is defined as percentage liver fat at six months minus percentage liver fat at baseline. The difference in mean change between metformin XR and placebo groups as well as its 95% confidence intervals will be calculated. The two-sample t-test will be used to compare groups. Sample Size and Power Calculations: Over a 1.5 year recruitment period, 44 subjects is a feasible recruitable sample size. We generally see at least 100 PCOS patients within our division per year. We also work closely with physicians in the Division of Adolescent Medicine and the Department of Obstetrics and Gynecology who will also serve as sources of study subjects for us. Forty-four subjects randomized 1:1 to metformin versus placebo provided greater than 80% power to detect a 1.4 standard deviation difference in the group average change from baseline to endpoint assuming a 5% type I error rate and an independent T-test. Preliminary data showing subjects with PCOS have an average of 4.8% liver fat, and assuming the average within subject change is less than 0.5+0.5% in the placebo group, the power calculations indicate the minimum detectable difference attributable to metformin treatment to be a 0.7% absolute, or a 15% relative decline in percentage liver fat. After the intent-to-treat analysis we will analyze the influence of partial compliance by adding cumulative dose exposure in to a multiple regression

model assessment of the group difference. Subjects will be stratified based on presence or absence of insulin resistance.

2. The association of percent liver fat with IR, dyslipidemia, VAT, total body adipose tissue, and markers of NAFLD and NASH will be estimated with correlation/regression and change in IR, dyslipidemia, and markers of NAFLD and NASH with change in percent liver fat following metformin with multiple regression. Sample Size and Power Calculations: 44 subjects provide 80% power and 5% alpha to detect a baseline association of liver fat with continuous measures of liver fat markers with r -values $> + 0.46$ when tested against H_0 of $r = + 0.10$. 20 subjects in the longitudinal study provides 80% power and 5% alpha to detect an incremental increase of 0.60 in model R^2 when percentage liver fat is added to treatment assignment to predict change in markers.

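### The longitudinal power figure in item 2 does not fit an R² increment: with 20 subjects, 0.60 has about 99% power, and the 80%-power increment is about 0.31 to 0.35

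*Combined protocol and SAP*

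**What the plan says.** Item 2 of the Statistical Analysis section plans to relate changes in insulin resistance, dyslipidemia and markers of NAFLD and NASH "with change in percent liver fat following metformin with multiple regression". The power statement for this analysis reads "20 subjects in the longitudinal study provides 80% power and 5% alpha to detect an incremental increase of 0.60 in model", where the metric named is R². The increment is the one that arises "when percentage liver fat is added to treatment assignment to predict change in markers".

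The sentence before it, for the cross-sectional analysis, is on the correlation scale: 44 subjects are to "detect a baseline association of liver fat with continuous measures of liver fat markers with r -values" above 0.46.

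The 20 subjects are not explained. Eligibility Criteria under Study Design describes the study "with the goal of recruiting 44 subjects", while paragraph a) Randomization says that subjects with raised liver fat or "insulin resistance on an oral glucose tolerance test (n=22) will be randomized to placebo or extended-release metformin".

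**The concern.** An R² increment of 0.60 means that liver fat alone accounts for 60 percentage points of the variance in the marker change, beyond treatment. That is a very large effect for one predictor, and 20 subjects would be expected to detect it with far more than 80% power. Either the number or its label therefore looked wrong.

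This is the plan's only power statement for the longitudinal association. A reader who takes it at face value would conclude that only an extreme association can be detected reliably, and might judge the analysis futile or give a null result too little weight.

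**Working it through.** **Inputs from item 2.** N = 20; alpha 5%; stated power 80%; stated increment ΔR² = 0.60; base model with treatment assignment (one term); one added term, liver fat. Whether that term is the level or the change in liver fat does not alter the count. Residual degrees of freedom are 20 − 3 = 17.

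**Input not given.** R₀², the R² of treatment alone. It is assumed to be 0, with 0.3 and 0.5 shown as a range.

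**Formulas.** Effect size f² = ΔR² / (1 − R₀² − ΔR²). Power is the probability that a noncentral F on 1 and N − 3 degrees of freedom exceeds the 5% critical value, which is 4.45 for 1 and 17.
- Fixed predictor: noncentrality λ = N·f².
- Random predictor, which is closer to the truth because liver fat is observed and not set by design: λ = f² times a chi-square on N − 2 degrees of freedom, with power averaged over that distribution.

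**Step 1: the plan's own figure.** With R₀² = 0, f² = 0.60 / 0.40 = 1.5 and, for a fixed predictor, λ = 20 × 1.5 = 30. Power is 99.9% (fixed) or 98.8% (random; a simulation of 40,000 trials gave 98.9%). Using 17·f² as the noncentrality gives 99.7%. The stated 80% does not reproduce.

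**Step 2: the increment with 80% power at N = 20.**

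| Assumed treatment-only R² | Fixed | Random |
|---|---|---|
| 0 | 0.31 | 0.35 |
| 0.3 | 0.21 | 0.25 |
| 0.5 | 0.15 | 0.18 |

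Check at R₀² = 0, fixed: f² = 0.3065 / 0.6935 = 0.442 and λ = 8.84, which gives 80%. Simulated power with a random predictor was 80.0% at 0.35 (R₀² = 0) and 80.0% at 0.245 (R₀² = 0.3). Zero is the assumption most favourable to the plan's figure, since every larger R₀² moves the increment further below 0.60.

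**Step 3: the sample size that an increment of 0.60 would need.** With R₀² = 0, the smallest N with at least 80% power is 9 for a fixed predictor (86.2%; N = 8 gives 78.9%) and 11 for a random one (82.5%; N = 10 gives 77.0%).

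**Step 4: is 0.60 a correlation?** The partial correlation is √[ΔR² / (1 − R₀²)]. At 80% power and N = 20 it is √0.3065 = 0.55 (fixed) or √0.3505 = 0.59 (random), whatever treatment explains. For a partial correlation of exactly 0.60, the Fisher transformation gives atanh(0.60) × √(20 − 1 − 3) = 0.693 × 4 = 2.77, hence power of 79.2%. The random-predictor calculation gives 81.4%, and the fixed-predictor calculation 88.5%. With R₀² = 0, a partial correlation of 0.60 is an increment of 0.60² = 0.36.

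**Step 5: dependence on the number followed** (80%-power increment, R₀² = 0).

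| N with six-month data | Fixed | Random |
|---|---|---|
| 20 | 0.31 | 0.35 |
| 22 | 0.28 | 0.32 |
| 36 (illustrative) | 0.19 | 0.20 |
| 44 (no loss) | 0.16 | 0.17 |

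**The case against.** The strongest reply is that the statement is safe: 20 subjects do give at least 80% power for an increment of 0.60. The reader is given a detectable value, only not the smallest one. That is true. The fault lies in presenting it as the value with 80% power.

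A second reply is that the model may hold more than the sentence says. Adding the insulin-resistance stratum as a covariate moves the 80%-power increment only to 0.308 (fixed) or 0.352 (random). Reading 0.60 as Cohen's f² gives 85% to 90% power, which is also not 80%. Bringing power at an increment of 0.60 down to 80% would take several added predictors, a far stricter alpha, or about half the subjects. The sentence states none of these.

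A third reply is that the correlation explanation is conjecture, and this stands. The match to 80% holds for the Fisher and random-predictor calculations, not for the fixed one (88.5%). About 10 or 11 subjects with a random predictor also come close to 80% for an increment of 0.60, so a near match does not identify the source. Only the author of the calculation can settle it.

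Finally, little depends on the figure. Item 2 is secondary, the study is a pilot, and the sample size is justified by recruitment feasibility and by item 1. This limits the weight of the point but does not make the figure correct.

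**Conclusion.** The concern holds. For 20 subjects, 5% alpha and one predictor added to treatment, an R² increment of 0.60 has 98.8% to 99.9% power, about 19 to 20 points above the stated 80%. The increment with 80% power is about 0.31 to 0.35, a little over half the stated value, if treatment alone explains nothing. That zero is an assumption, but no permissible value rescues 0.60.

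Mislabelling of a partial correlation is plausible and unconfirmed. The arithmetic is certain and the consequence small: the plan understates the sensitivity of a secondary analysis, and neither the primary t-test nor the sample size is affected. It is worth correcting, but it is not a reason to hold up the study.

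**What to change.** Go back to the original calculation, establish which metric was used, and replace the sentence with one of these:

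- If an R² increment was meant: *20 subjects give 80% power at 5% alpha to detect an R² increase of about 0.31 to 0.35 from adding percentage liver fat to treatment assignment, assuming treatment alone explains none of the variance.*
- If a correlation was meant: *20 subjects give 80% power at 5% alpha to detect a partial correlation of 0.60 between percentage liver fat and change in the marker, adjusted for treatment.*

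In both cases, name the method and the assumed treatment-only R² where it matters. Base the figure on the number expected to have six-month data, and say how 20 relates to the 44 subjects and to the n=22 under Randomization. If that number is not 20, the figures in both sentences must be recomputed; for the increment, the last table in the working gives values for 22, 36 and 44.

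The cost is one sentence of wording, with no change to the design, the sample size or the primary analysis.

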Pregnancy: Study subjects may begin ovulating or menstruating during the study as a response to metformin or naturally. Even if the study subject is not getting her period regularly or at all she will be instructed to always use a birth control method if she is sexually active. She cannot take a birth control pill if she is participating in this study so she should use a barrier method of birth control if she is sexually active. It is important to note that metformin is a category B drug in pregnancy, which means that its effects on a fetus are not fully known. Study subjects are instructed to call the study team as soon as possible if they think they may have become pregnant during the study.

Adverse events:

A serious adverse event associated with metformin use is lactic acidosis; however, this most commonly occurs in patients with congestive heart failure, renal failure and liver failure. We will be screening patients by questionnaire and with laboratory data in order to exclude those with underlying medical conditions. We will instruct patients to call immediately if they develop unexplained hyperventilation, myalgia. Malaise, unusual somnolence or other nonspecific symptoms.

We will be tracking the follow adverse event data at the 3 month and 6 month visits based on known common adverse events associated with metformin use: diarrhea, abdominal pain, nausea/vomiting, gas/bloating and any other side effect the subject may experience.

Potential Benefits:

Families and subjects will be provided with detailed analysis of body composition, OGTT and cardiovascular risk factor results and will be counseled about the implications for future metabolic complications, as well as on how to improve health through diet and exercise. All results will be provided to each subject's primary care physician and/or pediatric endocrinologist if directed by the subject's parents at time of study or later date.
